Fig. 2 . Dysregulation of GTPase targets. (A) Ovarian tumor tissue microarrays were purchased from US Biomax and stained for Cdc42 (pAb 10155-1-AP ProteinTech Group, Inc.). Tumor grade and type was confirmed, and immunoreactivity scoring was conducted by pathologist [name]. Statistical analyses show $p<0.001$ for low vs. high grade tumors, UNM Cancer Center Biostatistics core. (B) Primary tumor cDNA samples (TissueScan Disease Tissue qPCR Arrays, OriGene) were screened for Rac1b expression by qPCR. Normal vs. Gr. 2 $p<0.05$. (C) Rac1 and Cdc42 GTPase activities measured by GLISA in cells from fresh ovarian patient ascites or after 48 h in culture.

1.3 Drug Library Screening Predicts R-Enantiomers of Naproxen and Ketorolac as GTPase Inhibitors

Screening of the Prestwick library of FDA-approved molecules identified the R-enantiomer of naproxen as active against Rac1 and Cdc42, which we confirmed in cellular GLISA assays (Fig. 3A). R-, and S-ketorolac were identified for structure activity testing based on additional cheminformatics. Despite the common chemotype, S-naproxen and 6-MNA did not significantly inhibit Rac1 or Cdc42 **indicating that GTPase inhibition is independent of the COX pathway**. At nontoxic doses that are meaningful with respect to human serum levels at therapeutic doses (Table 1), the R-enantiomers of naproxen or ketorolac are more effective for inhibition of migration in OVCA 429 and SKOV3ip (Fig. 4A-B), and primary ovarian tumor cells isolated from ascites (not shown). The same structure activity relationship was observed for multicellular aggregate formation (Fig. 4C). Inhibition of proliferation was less marked (~50%) with R-naproxen>>S-naproxen. More than 20 other common NSAIDS were tested and did not detect inhibitory activity *in vitro* or in cells against Rac1 or Cdc42, nor any impact on ovarian cell migration or proliferation. *Thus, the structure activity relationships and selectivity suggest that the inhibitory actions of R-naproxen and R-ketorolac are due to an effect on novel Rac1 and Cdc42 GTPase targets as first revealed by the molecular library screen and predicted by cheminformatics.*

Virtual docking predicts that R-naproxen, but not S-naproxen can bind the GDP-bound pocket of Rac1 (Fig. 3B). In this model R-naproxen is stabilized through favorable H-bonds with Thr17 and Asp57, as

[figure not shown]

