10.1 Pre-treatment Sample Collection

- Collection of ascites cells at the time of tumor debulking
- Collection of peritoneal fluid and cells by the PI ([name]) or the co-PI's ([name] and [name]) and blood prior to ketorolac administration.

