10.3.4. Spreading, Adhesion, and Migration Assays of Patient Derived Peritoneal Cells

The impact of ketorolac treatment on residual ovarian tumor cell behavior will be assessed by measuring time for cell adhesion and spreading, as well as migration distance as follows. All of the assays require only small numbers of cells. CYTOO chips (see 5.6.5 and Fig. 7) will serve as an alternate measure for assessing cell adhesion and spreading. Controls: patient cell adhesion prior to treatment; cell adhesion when incubated with 100 μ M R-ketorolac.

10.3.4.1. Spreading: Cells (100-5,000/sample) will be rinsed in Dulbecco's PBS (DPBS) and plated on coverslips without or with extracellular matrix coating and images will be obtained at regular intervals. Spreading is defined as flattened cells without the refractile, fibroblastic morphology determined and expressed as a percentage of the total cells \pm SD.

10.3.4.2. Adhesion: Cells (100-5,000/well) will be plated onto 96 well plates without or with extracellular matrix coating and incubated for 30 min. Cells will be fixed and non-adherent cells will be removed by gentle washing. Colorimetric quantification of adherent cells will be performed using standard protocols.

10.3.4.3 Migration: Cells (100-5,000/sample) will be placed on collagen-coated coverslips in culture medium and migration will be measured by time lapse photography on a heated microscope stage (UNM Microscopy Facility). Distance traversed for individual cells will be quantified by image analysis software.

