11.2.2 Secondary Endpoints

We will determine the effect of IV ketorolac on cell adhesion and migration on ovarian cancer cells retrieved from the peritoneal cavity after cytoreductive surgery using several different biologic assays. Isolated cells will be tested for evidence of target inhibition and functional changes in adhesion and migration. Target activity assays: Rac1 and Cdc42 activity will be measured in cells using effector binding assays (GLISA) that are

commercially available (Cytoskeleton, Inc) and are used to determine activity of primary cells ex vivo as we have demonstrated in (Fig. 1C). In addition, we will conduct qRT-PCR analysis of cells isolated pre and post ketorolac administration to test for expression of genes downstream of Rac1 and Cdc42 activation that were validated in cell culture and in vivo studies. Adhesive properties of cells will be measured by assays for spreading and adhesion. For spreading analysis, cells will be rinsed in Dulbecco's PBS (DPBS) and plated on coverslips without or with extracellular matrix coating and images will be obtained at regular intervals. Spreading is defined as flattened cells without the refractile, fibroblastic morphology determined and expressed as a percentage of the total cells \pm SD as we've described previously (46). For adhesion, cells will be plated onto 96 well plates without or with extracellular matrix coating and incubated for 30 min. Cells will be fixed and non-adherent cells will be removed by gentle washing. Colorimetric quantification of adherent cells will be performed using standard protocols. Migration will be measured after plating cells on collagen-coated coverslips in assessing migration by time lapse photography on a heated microscope stage (UNM Microscopy Facility). Distance traversed for individual cells will be quantified by image analysis software. Data will be analyzed as a repeated measure ANOVA followed by Tukey's post hoc analysis in order to evaluate whether there are significant differences between groups (pre-and post-ketorolac treatment). Trend analyses of response will also be performed based on peritoneal R-ketorolac concentrations.

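### Spreading is scored as a percentage of all cells with no viability measure, so a fall in viability after baseline would be reported as reduced spreading

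*Combined protocol and SAP*

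**What the plan says.** Section 10.3.4.1 prepares the patient's peritoneal cells simply: "Cells (100-5,000/sample) will be rinsed in Dulbecco's PBS (DPBS) and plated on coverslips", with or without matrix coating, and images them at intervals. The outcome is binary per cell: "Spreading is defined as flattened cells without the refractile, fibroblastic morphology". It is "determined and expressed as a percentage of the total cells". Section 11.2.2 repeats this rule and refers to an earlier publication for the method.

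For migration, both sections say: "Distance traversed for individual cells will be quantified by image analysis software". No rule covers dead or immobile cells. For adhesion, section 10.3.4.2 says "Colorimetric quantification of adherent cells will be performed using standard protocols" and states no normalisation to viable cells plated. The point below rests on spreading, the only one of the three with a stated denominator.

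Section 10.3.4 lists its controls as "Controls: patient cell adhesion prior to treatment; cell adhesion when incubated with 100" μM R-ketorolac. Section 11.2.2 compares pre- and post-ketorolac samples by repeated-measures ANOVA with Tukey comparisons, with no viability term. The only threshold on patient cells is the minimum of more than 10,000 cells for PCR in section 10.3.5, which concerns quantity.

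Section 10.1 lists two pre-treatment collections. One is "Collection of ascites cells at the time of tumor debulking"; the other is peritoneal fluid and cells taken before the dose. The text does not say which is the baseline for these assays.

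**The concern.** The secondary objective is to show that ketorolac changes how ovarian cancer cells behave. Reported spreading, however, is the product of two quantities: the fraction of cells alive and the fraction of living cells that spread. The rule records only the product. A change in the first is then indistinguishable from a change in the second, and a fall goes in the direction that the plan would read as inhibition.

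The preclinical argument in section 1.3 carries a condition that would separate the two: inhibition was seen "At nontoxic doses that are meaningful with respect to human serum levels at therapeutic doses". The trial readout has no counterpart to it. Nor does the design separate them. The study is single-arm, so no untreated patient follows the same post-operative course, and time since surgery advances with time since dose. Viability that is not recorded when the cells are assayed cannot be recovered later, and only 7 to 10 complete sample sets are expected.

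**Working it through.** **Plan figures.** The documents give no viability, variance, effect-size or power figure for these assays. The only relevant number is the sample target in section 11.2.1, which reproduces: 60 × (1 − 0.60) = 24, against 25 stated; then 25 − 18 = 7 and 25 − 15 = 10 complete sets.

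**Formula.** Let v be the viable fraction and s the fraction of living cells that spread. Under the stated rule a dead cell counts as not spread, so

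reported spreading = v × s.

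Post-dose relative to baseline, the ratio is (v1/v0) × (s1/s0). If living cells do not change, s1 = s0 and the apparent change is v1/v0 − 1.

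**Illustration, with s = 60% throughout (assumed) and no drug effect.**

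| Viability, baseline to post-dose (assumed) | Reported spreading | Apparent relative change |
|---|---|---|
| 90% to 90% | 54% to 54% | 0 |
| 60% to 60% | 36% to 36% | 0 |
| 90% to 80% | 54% to 48% | −11% |
| 90% to 70% | 54% to 42% | −22% |
| 90% to 50% | 54% to 30% | −44% |
| 70% to 90% | 42% to 54% | +29% |

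The first two rows show that a constant dead fraction, high or low, creates no false change. The last row shows masking. If viability rises from 70% to 90%, living-cell spreading could drop from 60% to 0.42/0.90 = 46.7%, a real relative fall of 22%, and the reported figure would stay at 42%.

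**Effect on the planned test.** A simulation of the repeated-measures ANOVA used four time-points, 4,000 runs and no drug effect. Its assumptions were:

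- mean live-cell spreading 60%
- between-patient SD 10 points and within-patient SD 5 points, both on the live-cell percentage
- viability SD 5 points
- 100 cells per sample
- overall F test at 0.05 (the plan states no level)

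| Mean viability over the four time-points | Rejection, n = 7 | Rejection, n = 10 |
|---|---|---|
| constant at 90% or at 60% | about 5% | about 5% |
| 90/87/85/80% | 20% | 30% |
| 90/85/80/70% | 70% | 89% |
| 90/80/70/50% | about 100% | 100% |

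With viable cells as the denominator, rejection stayed between 4.7% and 5.8% in every scenario.

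These rates are sensitive to the inputs. For the Tukey comparison of predose with 24 h, I let the within-patient SD run from 5 to 10 points and applied it either to the live-cell or to the reported percentage, with viability SD 3 points. A 20-point fall in viability then gives significance in about 30% to over 99% of trials. A 10-point fall gives about 6% to just under 60%. Constant viability gives about 1%. The simulation shows that the mechanism can matter at this sample size; it does not estimate what this trial would see.

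**Migration.** If dead cells were tracked at about zero distance, mean distance would scale by v1/v0 in the same way. If the software or operator omits them, there is no such effect. The text does not settle which.

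**The case against.** The strongest reply is that the comparison is within patient, so only a change in viability matters, and nothing in the documents shows one. That stands, and it makes the point conditional. A reader might infer that dead post-operative cells will be read as inhibited cells. The documents do not support that. A constant dead fraction cancels, and the predose port sample is itself post-operative, so with that sample as baseline surgery does not separate the two sides. With the debulking ascites as baseline the comparison spans surgery and the risk is larger, but the plan does not name the baseline.

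A reader might also infer that migration is biased in the same way. The documents speak only of individual cells measured by image analysis and do not say that dead cells are tracked.

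The statement in section 1.3 about nontoxic doses weighs against drug cytotoxicity as a cause of a viability fall. It does not address time since surgery or handling.

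Other readouts offer partial checks. The fluid assays on cultured cells (10.3.2, 10.3.3) do not depend on patient-cell viability. Section 11.2.2 also plans a trend analysis on peritoneal R-ketorolac concentration. With the 5-hour R half-life in section 1.5.2, a single dose leaves 2^(−24/5), about 4%, of its plasma level at 24 h, so viability loss growing to 24 h would tend to run against that trend. Peritoneal kinetics are unknown, however, and neither check shows what happened to spreading in the patient's own living cells.

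Finally, section 11.2.2 cites a publication for the spreading method, and how total cells were counted there cannot be checked from these documents. The rule as written is all cells.

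**Conclusion.** The point holds for spreading, conditionally. The written rule uses all cells, no step measures viability, and no untreated group separates a viability change from a drug effect. Reported spreading therefore moves in proportion to any change in viability after baseline: 11% or 22% lower for falls from 90% to 80% or 70%, and upward if viability rises. These viabilities are assumptions, as is 60% spreading in the absolute figures. The documents give no viability data, so the actual size is unknown and may be nil. For migration the point is a question the text leaves open.

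It does not touch the primary concentration endpoint or the assays on immortalised cells. It concerns a secondary endpoint of a feasibility pilot. It should still be corrected, because without a viability record neither a positive nor a null spreading result could be defended.

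**What to change.** Amend sections 10.3.4 and 11.2.2 as follows.

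1. Apply a live/dead (dye-exclusion) stain to the plated cells at the end of imaging. Score spreading as a percentage of viable cells, and restrict migration tracks to cells viable at the end of imaging.
2. Where staining in place is not possible, record the viable fraction of the sample when yield allows and use it to adjust spreading (reported percentage divided by viable fraction; for example 42%/0.70 = 60%). A count on an aliquot gives only a fraction. It cannot show which plated cells or tracks are viable, so it is the fallback.
3. Report viability by time-point beside the functional readouts.
4. Name the predose port sample as the baseline for these pre/post comparisons.

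The cost is wording in two sections and a little bench work. Staining in place needs no extra cells. The fallback uses some, which matters because section 10.3.4 allows samples of as few as 100 cells. No extra patient sample is needed.

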10.3.5. PCR analysis of Patient Derived Peritoneal Cells

Genes downstream of Rac1 and Cdc42 activation, which have been validated in cell culture and through in vivo studies (e.g. PAK, IQGAP, DOCK-180, CRK, WAVE3) will be tested by quantitative real time PCR using human genome predesigned and validated primer sets and assay kits from Origene (Rockville, MD). Each assay will be performed in duplicate and ketorolac response will be established by comparison of pretreatment versus treatment samples. A >2-fold change between 0 treatment and subsequent treatment time-points

would be considered significant. This assay will be performed only when sufficient cell numbers are present in the peritoneal fluid (>10,000 cells) to allow purification of RNA.

11.0 STATISTICAL METHODS

11.1 Analysis of Demographic and Baseline Characteristics

The analysis of demographic characteristics (age, gender, tobacco abuse history and ethnicity) and baseline characteristics, including weight change, performance status, and histologic subtype, will be primarily descriptive.

11.2 Endpoint Analyses

11.2.1 Primary Endpoint and Sample Size

Ketorolac availability, concentration and racemic mixture of Toradol® ([R,S]-ketorolac) in the peritoneal cavity. Intraperitoneal concentration and racemic mixture of ketorolac is currently unknown although serum pharmacokinetic data suggests a slower clearance of the R-racemate. The **primary objective** of this study is to determine the concentration of measurable levels of R and S- Ketorolac (and the percent racemic mixture) in the peritoneal cavity after IV administration in the post-operative patient after cytoreductive surgery. Since this is a pilot trial for feasibility of obtaining the desired measures, a true sample size calculation is difficult to assess. We anticipate that we will need to recruit 60 patients pre-operatively who meet the first phase of eligibility. We anticipate that 60% will have a diagnosis other than advanced stage invasive epithelial ovarian cancer, fail optimal debulking, have a clinical decision to not proceed with a port placement or not enough ascites or negative cytology of the ascites that will warrant no further participation in the study. This data is based on our initial experience with the first 12 patients enrolled on the trial. We then anticipate that 25 patients will have intraoperative port placement and be eligible for secondary eligibility. We anticipate that an additional 15-18 patients will either fail secondary eligibility, decline sample collection, decline ketorolac or have indications to withhold ketorolac, decline blood sampling, have inadequate re-accumulated fluid for sampling, or failed extraction of ascites samples from the port. The sample target remains 7-10 complete sets of blood and ascites samples for primary and secondary endpoint analyses.

Data will be analyzed as a repeated measure ANOVA followed by Tukey's post hoc analysis in order to evaluate whether there are significant differences between groups (pre-and post-ketorolac treatment). We plan to group both dose groups together as we anticipate similar drug measures based on known prior serum pharmacokinetic studies. If we find a large discrepancy in peritoneal ketorolac concentrations between the 15mg and 30mg treated group, we may amend the protocol to increase sample size to evaluate the groups independently. The analysis of demographic characteristics (age and ethnicity) and clinical characteristics, including histologic tumor type, and stage of disease will be descriptive. For the peritoneal distribution study, seven patients should be sufficient for statistically meaningful results based on a study of similar design to measure concentration of doxorubicin in ovarian ascites following IV administration (45).

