1.5.2. Ketorolac Pharmacology and Pharmacokinetics

Ketorolac tromethamine is a non-steroidal anti-inflammatory drug. The biological activity of Ketorolac tromethamine for pain relief is associated with the S-form. The peak analgesic effect of Ketorolac tromethamine occurs within 2 to 3 hours and is not statistically significantly different over the recommended dosage range of Ketorolac tromethamine. The greatest difference between large and small doses of Ketorolac tromethamine is in the duration of analgesia.

Ketorolac tromethamine is a racemic mixture of [-S]- and [+R]-enantiomeric forms, with the S-form having analgesic activity and the R-form the proposed cancer inhibition effect. The IV dosing of ketorolac is 100% bioavailable. The pharmacokinetic parameters for IV dosing is shown in Table 2. In adults, following IV administration of Ketorolac tromethamine in the recommended dosage ranges, the clearance of the racemate does not change. This implies that the pharmacokinetics of Ketorolac tromethamine in adults, following single or multiple IV doses of Ketorolac tromethamine are linear. At the higher recommended doses, there is a proportional increase in the concentrations of free and bound racemate.

The mean apparent volume ($V\beta$) of Ketorolac tromethamine following complete distribution was approximately 13 liters. This parameter was determined from single-dose data. The Ketorolac tromethamine racemate has been shown to be highly protein bound (99%). Nevertheless, plasma concentrations as high as 10 mcg/mL will only occupy approximately 5% of the albumin binding sites. Thus, the unbound fraction for each enantiomer will be constant over the therapeutic range. A decrease in serum albumin, however, will result in

increased free drug concentrations. The half-life of the Ketorolac tromethamine S-enantiomer was approximately 2.5 hours ($SD \pm 0.4$) compared with 5 hours ($SD \pm 1.7$) for the R-enantiomer. In other studies, the half-life for the racemate has been reported to lie within the range of 5 to 6 hours.

	Tmax (min)	Cmax (mcg/ml) single dose	Cmax (mcg/ml) steady state qid	Cmin (mcg/ml) steady state qid	Cavg (mcg/ml) steady state qid
15 mg	1.1 \pm 0.7	2.47 \pm 0.51	3.09 \pm 0.1.17	0.61 \pm 0.21	1.09 \pm 0.30
30 mg	2.9 \pm 1.8	4.65 \pm 0.7	6.85 \pm 0.7	1.04 \pm 0.7	2.17 \pm 0.7
Tmax = time to peak plasma concentration, Cmax = peak plasma concentration, Cmin = trough plasma concentration, Cavg = average plasma concentration					

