Table 2. Average Pharmacokinetic Parameters for IV Ketorolac

The intraperitoneal distribution of ketorolac and its racemic mixture is unknown and represents the primary endpoint of this trial. Based on the known pharmacokinetics, it is favorable that the half-life of the R-enantiomer is longer and that both are protein bound. We anticipate that the post-op decrease in serum albumin will favor free drug with a high rate of transport into the peritoneal cavity.

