2.0 OBJECTIVES

2.1 Primary Objective

The primary objective of this study is to determine the concentration of measurable levels of R and S- Ketorolac (and the percent racemic mixture) in the peritoneal cavity after IV administration in the post-operative patient after cytoreductive surgery.

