4.2 Exclusion Criteria

Patients meeting any of the following criteria are ineligible for study entry:

- Non-epithelial ovarian cancer or metastatic cancer to the ovaries
- Borderline ovarian cancer without ascites
- Presumed early stage ovarian cancer
- No clinical indication for a peritoneal port
- Active use of an epidural catheter
- Uncontrolled or unstable medical conditions
- Off study use of ketorolac or other NSAIDs prior to study administration
- Active bleeding or high risk of bleeding
- Active therapeutic anticoagulation
- Known hypersensitivity to NSAIDs
- Chronic or acute renal insufficiency as defined by a preoperative serum creatinine greater than 1.5mg/dL or creatinine clearance of < 60 ml/min
- Any co-morbid condition that, in the view of the attending physician, renders the patient at high risk from treatment complications

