10.3.1 Ketorolac Concentration in Peritoneal Fluid - HPLC

Peritoneal concentrations of the R(-) and S(+) enantiomers of ketorolac will be determined by using published procedures for measuring plasma concentrations (44). High pressure liquid chromatography will be performed using UV detection at 313 nm. Standards will be prepared at 7 ketorolac plasma concentrations using 100 μ L steroid-free plasma to attain final concentrations of 0.025, 0.05, 0.10, 0.25, 0.5, 1.0, and 2.0 μ g/mL. Peritoneal samples (100 μ L) and standards will be added to silanized tubes containing the internal standard, loxapine HCL. Before extraction with 4 mL of methyl tert-butyl ether, proteins will be precipitated with 30 μ L of 10% weight to volume solution of trichloroacetic acid. Samples will be shaken for 10 min, centrifuged for 10 min, and the organic layer transferred to silanized culture tubes and evaporated under nitrogen. Mobile phase (50 μ L) will be added, the samples then will be transferred to autosampler vials, and 30 μ L will be injected onto the high pressure liquid chromatography column. Baseline separation of the isomers will be achieved using a chiral column (Astec Chirobiotic R (250 _ 4.6 mm²) obtained from Advanced Separation Technologies, Inc. Whippany, NJ) using a binary gradient mobile phase of 0.07 g ammonium formate and 24 μ L glacial acetic acid per liter methanol and increasing to 100% methanol for 17.5 min at a flow rate of 1.0 mL/min. Samples will be performed in duplicate.

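### The primary analysis of peritoneal ketorolac is a pre- versus post-dose test, which does not estimate R or S levels and cannot address percent R; per-time estimates with intervals should replace it

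*Combined protocol and SAP*

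**What the plan says.** Section 2.1 sets the primary objective: to "determine the concentration of measurable levels of R and S- Ketorolac (and the percent racemic mixture) in the peritoneal cavity". Section 1.5.2 gives the reason: "The intraperitoneal distribution of ketorolac and its racemic mixture is unknown and represents the primary endpoint of this trial". Section 11.2.1 repeats that "Intraperitoneal concentration and racemic mixture of ketorolac is currently unknown" and opens by listing availability alongside concentration and racemic mixture.

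For this endpoint, Section 11.2.1 names one inferential method, a repeated-measures ANOVA followed by Tukey's test, whose purpose is to "evaluate whether there are significant differences between groups (pre-and post-ketorolac treatment". The same sentence is used in Section 11.2.2 for the cell assays. Section 11.2.1 pools the 15 mg and 30 mg patients and allows for an amendment if their levels turn out very different. Descriptive analysis is mentioned only for demographic and clinical characteristics.

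Three other places matter:
- Section 4.2 excludes "Off study use of ketorolac or other NSAIDs prior to study administration".
- Section 10.3.1 gives the assay standards as "final concentrations of 0.025, 0.05, 0.10, 0.25, 0.5, 1.0, and 2.0" mcg/mL, with no rule for values below the lowest.
- Section 11.2.2 uses the measured levels again: "Trend analyses of response will also be performed based on peritoneal R-ketorolac concentrations".

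**The concern.** The objective asks for quantities: how much R, how much S, and in what proportion. The stated analysis asks whether post-dose differs from pre-dose. No summary statistic, interval, analysis of percent R or below-limit rule is given for the concentration endpoint.

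What is at stake is the content of the primary result. A p-value against a near-zero baseline says little about level and nothing about enantiomer mix. If the scale and below-limit rule are chosen after the data are seen, whether R counts as still present at 24 h may turn on that choice. Persistence of R is part of the trial's rationale, since Section 1.5.2 calls its longer half-life favourable.

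**Working it through.** **1. Sample size used.** Section 11.2.1 recruits 60 and expects to lose 60%: 60 × 0.40 = 24, against 25 stated. It then loses 15-18: 25 − 18 = 7 and 25 − 15 = 10. The target of 7-10 complete sets therefore reproduces. The statement that seven patients suffice cannot be checked, because no SD, effect, alpha or precision is given.

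**2. Percent R (no model needed).** Percent R = 100 × R/(R + S). With no drug before dosing this is 0/0, so a pre/post contrast is undefined.

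**3. Illustrative model.** The plan gives no peritoneal levels, so plasma kinetics stand in.
- From Section 1.5.2: half-lives R 5 h (SD 1.7) and S 2.5 h (SD 0.4); a distribution volume that "following complete distribution was approximately 13 liters"; Cmax 4.65 mcg/mL after 30 mg (Table 2).
- Assumed: n = 7, single dose, 30% of patients on 15 mg, CV 30% between and 20% within patients, peritoneal/plasma ratio 1, limit 0.025 mcg/mL (lowest standard), alpha 0.05. Values below the limit become 0 on the raw scale and 0.0125 before taking logs.

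Each enantiomer starts at 15 mg / 13 L = 1.15 mcg/mL and falls as 2^(−t/half-life):

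| Time | R (mcg/mL) | S (mcg/mL) | Percent R |
|---|---|---|---|
| 1 h | 1.00 | 0.87 | 53.5 |
| 6 h | 0.50 | 0.22 | 69.7 |
| 24 h | 0.041 | 0.0015 | 96.5 |

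The volume implies an initial racemate level of 30/13 = 2.31 mcg/mL, half of the Table 2 Cmax. Anchoring to Cmax doubles the levels and leaves percent R unchanged.

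**4. The stated test.** With times 0, 1, 6 and 24 h, Tukey calls a time different from pre-dose if the mean difference exceeds q × √(MSE/n), where q(0.95; 4, 18) = 4.00. Over 20,000 simulated trials (ranges cover three ways of drawing the half-life):

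| Contrast with pre-dose | Raw scale | Log scale | Patients quantifiable |
|---|---|---|---|
| R and S, 1 h | 100% | 100% | about 100% |
| R, 6 h | 89-93% | 100% | about 100% |
| S, 6 h | 24-26% | 100% | over 99% |
| R, 24 h | 0% | 59-74% | 51-59% |
| S, 24 h | 0% | 0% | at most 0.1% |

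Anchored to Cmax, R at 24 h is 0% raw and 92-97% log. At n = 10 with V = 13 L it is 0% and 80-92%, and S at 6 h is 43-46% raw.

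The raw-scale result for S at 6 h has a simple cause. The mean dose factor is 0.7 × 1 + 0.3 × 0.5 = 0.85, so the expected difference is about 0.85 × 0.22 = 0.19. The threshold is 4.00 × √(MSE/7) = 1.51 × √MSE, so √MSE must be below about 0.12. The pooled error is dominated by the larger, more variable 1 h values and usually exceeds that.

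**5. How firm is the 1 h result?** For R at n = 7 with V = 13 L on the raw scale:
- By peritoneal/plasma ratio, rejection is 100% at 0.1, 98% at 0.05, 60-69% at 0.03, 6-10% at 0.02 and 0% at 0.01.
- With the 1 h level cut by slow uptake to a half, a quarter or an eighth, it is 99.9%, 88% and 18%.

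**6. Multiple dosing.** After doses at 0, 6, 12 and 18 h, model R at 24 h is 1 + 2^(6/5) + 2^(12/5) + 2^(18/5) = 1 + 2.30 + 5.28 + 12.13 = 20.7 times the single-dose value. An unlabelled mixture at 24 h is not interpretable.

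**7. What estimation would give.**
- Number quantifiable, exact 95% interval: 7/7 gives 59-100%, 4/7 gives 18-90%, 0/7 gives 0-41%.
- Geometric mean: factor exp(t × √ln(1 + CV²)/√n). For an assumed total CV of 50% at n = 7: exp(2.447 × 0.472/2.646) = 1.55. For CV 30-100% the factor is 1.31-2.16 at n = 7 and 1.23-1.81 at n = 10.
- Percent R at 6 h: log(R/S) = (6/5) × ln 2 = 0.832 with model SD 0.49. At n = 7 the half-width is 2.447 × 0.49/√7 = 0.453, so the limits 0.379 and 1.285 convert to 59% and 78%.

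**The case against.** Section 11.2.1 lists availability as part of the primary endpoint, and peritoneal distribution is unknown, so a comparison of post-dose with pre-dose fluid does bear on something the trial wants to know. That stands. A reader might infer that the analysis answers a question the trial never asked; the documents do not support this. The analysis is incomplete for the stated endpoint.

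A reader might also infer that rejection at 1 h is a foregone conclusion. That is too strong. Ketorolac is 99% protein bound (Section 1.5.2), the peritoneal/plasma ratio is unknown, and step 5 shows that the result fails at low ratios or with slow uptake.

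Nor is the ANOVA model incapable of handling percent R in any form. It could compare percent R between post-dose times, but that is not its stated purpose and would not estimate percent R at any time.

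Finally, the model percentages rest on plasma kinetics and assumed variability, and this is a small feasibility pilot. Both points limit how much weight the numbers can carry. They do not touch the textual gap, and pilots too are best reported as estimates with intervals.

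**Conclusion.** The concern holds in a limited form and should be fixed. From the text alone, the stated primary analysis compares post-dose levels with an essentially zero baseline, bears at most on availability, gives no estimate of R or S, and cannot address percent R.

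The rest is conditional. Rejection at 1 h is near certain only if drug reaches the peritoneum promptly and, with V = 13 L, at a peritoneal/plasma ratio of about 0.05 or more; anchoring to Cmax roughly halves that ratio. The later results depend on the unstated scale and below-limit rule. The sizes shown (S at 6 h about 24% against 100%; R at 24 h 0% against about 60-70%) illustrate that dependence under plasma-proxy assumptions and are not forecasts.

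The harm is modest. Concentrations will still be measured, no success rule uses the p-value, and the data can be re-analysed.

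**What to change.** In Section 11.2.1, make estimation at each post-dose time the primary analysis, using every sample collected:

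- (a) Report number quantifiable over number sampled, with an exact 95% interval. This answers availability.
- (b) Report geometric means of R and of S with 95% intervals on the log scale, where more than half of the values are at or above 0.025 mcg/mL. Otherwise report only the number quantifiable and the range. Show individual values and results by dose (15 mg, 30 mg). Dose-normalise or dose-adjust any pooled estimate: Table 2 Cmax already differs by 4.65/2.47 = 1.88-fold.
- (c) Report paired log(R/S) with a 95% interval, converted to percent R, where both enantiomers are quantifiable, and a lower bound where only R is.
- (d) Use the pre-dose sample as an assay blank.
- (e) Show 24 h data by number of doses received.

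Label any censored-likelihood interval for R at 24 h as approximate: in the model its coverage was 89% at n = 7 and 85% at n = 10 with V = 13 L (94% at n = 7 anchored to Cmax). If ANOVA/Tukey is kept for concentrations, make it secondary and fix its scale and below-limit rule before data are seen. It can stay for the cell assays in Section 11.2.2.

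Separately, Section 9.2 lists need for additional ketorolac during collection as a reason for discontinuation, while Sections 9.0 and 10.2 provide for multiple dosing and a later sample. These must be reconciled.

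The cost is revised wording and a little more analysis, with no extra patients or samples. Intervals will be wide at 7-10 patients, and dose subgroups (about 0.3 × 7 = 2 patients on 15 mg under the assumed mix) may support little beyond individual values.
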